1.1.3. Overall Design

This is a double-blind, randomized, placebo-controlled study of DCR-AUD to evaluate the safety, tolerability, PK, and PD of repeat doses of DCR-AUD in adult HVs.

Participants will receive 3 injections of study intervention (Day 1, Day 29, and Day 57), and have assessment visits through Week 24. Up to 10 EIAs will be conducted over the 24-week period to characterize the PD of DCR-AUD. For each EIA, participants will consume 4 standard drinks over the course of 80 minutes. Participants will be admitted to the clinic overnight for each EIA. At the discretion of the Investigator, participants who present with increasing positive ethanol reaction symptoms at the Day 169 EIA (flushing, headache, lightheadedness, palpitations, nausea, or vomiting) will be followed for an additional 4 weeks (through Day 197).

Table 1 presents the schedule of activities for the Screening, Dosing, End of Study, and Conditional Follow-up Visits. **Table 2** presents the schedule of activities for interim visits at which no study drug is administered. **Table 3** presents the schedule of activities for the EIA.

Number of Participants:

16 participants are planned for enrollment.

Intervention Groups and Duration:

Participants will be randomized 3 to 1 to DCR-AUD or placebo, administered at a dose of 480 mg once every 4 weeks at Days 1, 29, and 57.

Individual participants will be screened for a period of up to 4 weeks. Randomization and administration of the first dose of study intervention will occur on Day 1. Participants will return to the site for safety, tolerability, PK, and PD monitoring at specified time points as per the Schedule of Activities. Participants will be followed for approximately 24 weeks after the first injection of study intervention.

Study Population Key Criteria:

[figure not shown]
- Overtly healthy men and women aged 21 to 65 years.
- No diagnosis of AUD within the preceding 12 months per Diagnostic and Statistical Manual of Mental Disorders (DSM-5).
- Social drinkers who consume, on average, 5 to 20 drinks per week for men or 5 to 14 drinks per week for women over the 4 weeks prior to screening, and not more than 8 drinks in a single day.
- No evidence of overt or sub-clinical hepatic pathology, as manifest by serologic tests demonstrating hepatic inflammation or compromised hepatic synthetic function.
- No history of substance use disorder (SUD) or illicit drug use (excluding cannabis) within the preceding 12 months.

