- ^m Participants may be discharged from clinic following collection of the 24-hour postdose PK sample. Participants will return to clinic for collection of PK samples at 72 hours postdose on Days 4 and 32.
- ⁿ EIA will be conducted on the first day of the visit once all other assessments for that day have been completed. A total of 10 EIAs will be conducted. The timing of assessments and ethanol administration are detailed in [Table 3](#).
- ^o On dosing days, ECGs will be conducted approximately 30 minutes predose and 15-to-30 minutes postdose. If multiple assessments are due, the order of assessment should be ECG, vitals, PK, and then other assessments; with PK sample collection occurring at the nominal time. At Screening and EOS, one ECG will be performed. Screening ECGs may be repeated one time for determination of eligibility.
- ^p Blood pressure, if out of range at Screening, may be repeated one time for determination of eligibility.
- ^q Blood pressure and pulse rate to be recorded 15 (\pm 5) minutes postdose.
- ^r Height will be measured and recorded at Screening. Weight will be measured and recorded at every visit.
- ^s Sample to be collected prior to ethanol administration.
- ^t Hematology to include complete blood count with differential and RBC indices. See [Section 10.2](#) for a complete list of parameters.
- ^u See [Section 10.2](#) for a complete list of parameters.
- ^v Blood samples for complement testing to be collected predose and 2, 8, and 24 hours postdose on Day 1 and Day 57.
- ^w Blood sample for ADA testing to be drawn at same time as predose PK sample on Day 1.
- ^x Plasma samples for PK analysis to be collected predose and at 1, 2, 4, 6, 8, 24, and 72 hours postdose (exception: no 72-hour PK sample is required at Day 57). A single sample will be collected on Day 168. If multiple assessments are due, the order of testing should be ECG, vitals, PK, and then other assessments, with the PK sampling performed preferably at the nominal time point. A \pm 15-minute window will be allowed for collections at 1, 2, 4, 6, and 8 hours postdose. A \pm 30-minute window will be allowed for collection at 24 hours postdose. A \pm 60-minute window will be allowed for collection at 72 hours postdose.
- ^y Participants to record any symptoms associated with use of alcohol outside of in-clinic EIAs. Diary to be issued at time of discharge from clinic and collected and reviewed upon return to clinic.

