3.2.7 Pharmacokinetic Variables

Pharmacokinetic concentration data will be obtained at time point(s) described in the protocol version 2.0 as follows:

PK concentrations of DCR-AUD will be determined at the following nominal times: 0 (pre-dose) and at 1, 2, 4, 6, 8, 24, and 72 hours post-dose on days 1, 29, 57 (exception: no 72-hour PK sample is required on Day 57). A single sample will be collected on Days 1, 14, 42, 70, and 168 along with the ADA samples. These single PK concentrations maybe used for deriving the PK parameters, if the concentrations are detectable.

Derivation of PK parameters will be the responsibility of CPMS group, [REDACTED].

If calculable, the following PK parameters listed in [Table 3-2](#) will be determined for DCR-AUD in plasma following single subcutaneous (SC) dose administration.

Table 3-2 Plasma Pharmacokinetic Parameters After Each Dose Administration of Multiple Dose Study

Parameter	WNL Name	CDISC Name	Definition
C _{max}	Cmax	CMAX	Maximum observed concentration
C _{last}	Clast	CLST	Last measurable concentration
C _{min}	Cmin	CMIN	Minimum observed concentration in a dosing interval after last dose administration
t _{max}	Tmax	TMAX	Time corresponding to occurrence of C _{max}
t _½	HL_Lambda_z	LAMZHL	Apparent terminal elimination half-life
λ _z	Lambda_z	LAMZ	Terminal elimination rate constant
AUC _{0-last}	AUClast	AUCLST	Observed AUC from time zero to the last quantifiable concentration
AUC _{0-t}	AUCT	AUCINT(0-X)	Observed AUC from time zero to some fixed time t (i.e., AUC ₂₄ or AUC ₄₈)
AUC _{0-inf}	AUCINF_obs	AUCIFO	AUC from time zero extrapolated to infinity
%AUC _{ex}	AUC_%Extrap_obs	AUCPEO	Percentage of AUC _{0-inf} obtained by extrapolation beyond t _{last}

Parameter	WNL Name	CDISC Name	Definition
CL/F	Cl_F_obs	CLFO	Apparent clearance following SC administration
V _z /F	Vz_F_obs	VZFO	Apparent volume of distribution during terminal phase

Source: NCI EVS Terminology Resources website:
<http://www.cancer.gov/cancertopics/cancerlibrary/terminologyresources/cdisc>.

Approved

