AUC_{0-x}	
The AUC from zero time to the specific time x is the sum of areas up to the specific time x sample (no extrapolation will be applied):
 $AUC_{0-x} = AUC_{0-x} = \int_0^x C_x * dx$
AUC_{0-tau}	
The AUC over the dosing interval will be determined for multiple dose studies using the trapezoidal rule, as stated above. Calculated for days 1, 29 and 57.

AUC_{0-inf}	
The area from zero time extrapolated to infinite time will be calculated as follows:
 $AUC_{0-inf} = AUC_{0-t} + \frac{C_{last}}{\lambda_z}$ 
where C_{last} is the last observed quantifiable concentration. Calculated for days 1, 29, and 57.

$\%AUC_{ex}$	
The percentage of AUC_{0-inf} obtained by extrapolation will be calculated as follows:
 $\%AUC_{ex} = \frac{AUC_{0-inf} - AUC_{0-t}}{AUC_{0-inf}} \times 100$ 
Unless otherwise determined by PK Scientist's best knowledge and judgment, if the $\%AUC_{ex}$ is greater than 20% the value, $\%AUC_{ex}$, and all dependent parameters (i.e., AUC_{0-inf}, MRT, Vz and CL) will be flagged in listings and excluded from summary tables and statistical analysis of PK parameters. The reason for exclusion will be listed/footnoted in parameter listings.

λ_z and $t_{1/2}$	
 1. The apparent terminal phase rate-constant (λ_z) will be estimated by linear regression of concentration versus time data presented in a log-linear scale. 2. Data are primarily monotonically decreasing in magnitude and are representative of the actual decline in the log concentration-time curve. 3. Only those data points that are judged to describe the terminal log-linear decline will be used in the regression. 4. A minimum number of three data points in the terminal phase will be used in calculating λ_z with the line of regression starting at any post-C_{max} data point (C_{max} should not be part of the regression slope). Unless otherwise determined by PK Scientist's best knowledge and judgment or if instructed by the Sponsor, if the adjusted correlation coefficient (R^2 adjusted) is <0.9, then λ_z and all the λ_z dependent

Parameter	Guideline for Derivation

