	
parameters (i.e. $t_{1/2}$, $AUC_{0-\infty}$, CL, MRT, and V_z) will be flagged in listings and excluded accordingly from summary tables and statistical analysis of PK parameters. The reason for exclusion will be listed/footnoted in parameter listings.
 
5. Unless otherwise determined by PK Scientist's best knowledge and judgment, the interval used to determine λ_z should be equal or greater than 1.5-fold the estimated $t_{1/2}$, and if less than 1.5-fold, λ_z will be flagged in listings and might be excluded from summary tables and statistical analysis of PK parameters. All the derived parameters (i.e. $t_{1/2}$, $AUC_{0-\infty}$, CL, MRT, and V_z) may also be flagged in listings and excluded from statistical analysis of PK parameters. The reason for exclusion will be listed/footnoted in parameter listings.
 
6. The $t_{1/2}$ will be calculated as follows:
 $t_{1/2} = \ln 2 / \lambda_z = 0.693 / \lambda_z$ 
7. Data points may be dropped from the linear regression if the PK Scientist considers the reported values to be anomalous. Any data points so designated should remain in the listings with a footnote and be identified in the study report with a rationale for exclusion.

CL or CL/F	
Apparent clearance (CL/F) following extravascular (e.g. SC) dosing will be calculated as:
 $CL/F = \frac{Dose}{AUC_{0-\tau}} / F$ 
In the case of steady state administration $AUC_{0-\tau}$ will be the denominator.

V_z/F	
Volume of distribution at terminal phase following extravascular (SC) dosing may be calculated from:
 $V_z/F = \frac{Dose}{\lambda_z \times AUC_{0-\tau}} / F = (CL/F) / \lambda_z$ 
Likewise, if derived for steady state administration $AUC_{0-\tau}$ will be used.

R_{ac}	
Accumulation ratio, calculated from comparison of single dose and steady state data:
 $R_{acAUC} = \frac{Steady\ state\ AUC_{0-\tau}}{Single\ dose\ AUC_{0-\tau}}$ $R_{acCmax} = Steady\ state\ C_{max} / Single\ dose\ C_{max}$ 
Day 1 represents single dose and day 57 represents steady state.

PK Parameters Listings:

PK parameters will be listed by participant for the SP. PK parameters that will be flagged and/or excluded from summary tables and statistical analyses of PK parameters will be flagged and footnoted with the reason for flagging/exclusion.

PK Parameter Summary Tables:

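### With unchanged exposure, the AUC accumulation ratio can fall below 1, because intensive sampling ends at 24 h on Day 57 but at 72 h on Day 1 and the SAP sets no common end time

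*SAP*

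**What the plan says.** - **Definition.** SAP 4.12.2, Table 4-1, describes Rac as "Accumulation ratio, calculated from comparison of single dose and steady state data". The AUC version is the steady-state AUC0-tau over the single-dose AUC0-tau, and "Day 1 represents single dose and day 57 represents steady state". A Cmax version is defined alongside it.
- **Interval.** Protocol 1.1.3 has study drug "administered at a dose of 480 mg once every 4 weeks at Days 1, 29, and 57", so tau is 28 × 24 = 672 h.
- **AUC rule.** For AUC0-tau the SAP says: "The AUC over the dosing interval will be determined for multiple dose studies using the trapezoidal rule, as stated above". The rule above it in the table is linear-up/log-down, stops at the last quantifiable sample and rules out extrapolation. Terminal values below the quantification limit (BLQ) are set to missing.
- **Intensive sampling.** Predose, 1, 2, 4, 6, 8, 24 and 72 h, with the "exception: no 72-hour PK sample is required on Day 57" (SAP 3.2.7). The protocol's Schedule of Activities agrees: "Participants will return to clinic for collection of PK samples at 72 hours postdose on Days 4 and 32".
- **Sparse sampling.** "A single sample will be collected on Days 1, 14, 42, 70, and 168 along with the ADA samples" (SAP 3.2.7). On their use: "These single PK concentrations maybe used for deriving the PK parameters, if the concentrations are detectable".
- **A common-window AUC is already available.** SAP Table 3-2 lists an AUC to a fixed time, with 24 h as one example. It lists neither AUC0-tau nor Rac.

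**The concern.** Numerator and denominator carry the same label, AUC0-tau, but the schedule and the area rule need not deliver the same window on the two days. The Day 1 interval has a 72 h sample and is closed by the Day 29 predose sample at 672 h. The Day 57 interval has no 72 h sample and nothing at 672 h. The only possible link beyond 24 h is the Day 70 sample, and its use is left open. The SAP sets no common end time for the ratio and no rule for when the last quantifiable times differ.

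PK after repeat dosing is a secondary objective. A ratio of 0.7 produced by truncation would look like falling exposure. SAP 4.12.2 also uses AUC0-tau as the denominator for steady-state CL/F, and Vz/F follows from it, so a Day 57 area cut at 24 h would raise both.

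**Working it through.** The documents state no accumulation ratio, half-life or quantification limit, so there is no planned figure to reproduce. The check gives both days the same concentration curve and asks what the SAP's rule returns.

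**Step 1: true ratio.** With linear kinetics and three doses, the third-interval AUC over the first is (1 − 2^(−3·672/h)) / (1 − 2^(−672/h)), where h is the half-life in hours. At h = 72 this is 1.0016. For the shorter half-lives used here it is 1.00.

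**Step 2: closed form.** For a mono-exponential curve cut at 24 h on Day 57 and at 72 h on Day 1, the ratio is (1 − 2^(−24/h)) / (1 − 2^(−72/h)). For h = 5, 8, 12 and 24 it is 0.964, 0.877, 0.762 and 0.571.

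**Step 3: scheduled times.** This uses a one-compartment subcutaneous curve, assumed absorption half-life 1–2 h, and linear-up/log-down trapezoids. Example with half-life 12 h and absorption half-life 1 h (arbitrary concentration units):
- Concentrations at 0, 1, 2, 4, 6, 8, 24 and 72 h: 0, 0.484, 0.699, 0.798, 0.754, 0.683, 0.2727, 0.0170.
- AUC0-24 = 0.242 + 0.592 + 1.497 + 1.552 + 1.436 + 7.150 = 12.469.
- 24–72 h segment = 48 × (0.2727 − 0.0170) / ln(0.2727/0.0170) = 4.426.
- Ratio = 12.469 / (12.469 + 4.426) = 0.738.

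| Assumed half-life | Ratio, 24 h vs 72 h | 72 h level as % of Cmax |
|---|---|---|
| 5 h | 0.94–0.95 | about 0.01 |
| 8 h | 0.83–0.86 | 0.3–0.4 |
| 12 h | 0.71–0.74 | 2.1–2.7 |
| 24 h | 0.52–0.55 | 15–17 |

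**Step 4: when it does not happen.**
- *72 h BLQ on Day 1:* both areas end at 24 h and the ratio is 1.00. At a 5 h half-life this is quite possible.
- *Day 14 and Day 70 both quantifiable and used:* each falls 13 days (312 h) after its dose, so the windows match. The ratio is then 1.00 for one-compartment curves. For curves with 4 h and 60 h phases (5–20% slow) it is about 1.03–1.12, because the Day 57 area bridges 24 to 312 h in one step. If the Day 29 predose sample is also quantifiable, Day 1 extends to 672 h; at a 72 h half-life that gives 0.95.

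**Step 5: extrapolating both days to 672 h** (terminal slope from the last three points; not what the SAP describes). One-compartment curves give 1.00–1.06 at half-lives of 5–12 h and 1.01–1.19 at 24 h. The 4 h/60 h curves remain at about 0.6–0.8, and milder biphasic examples (2–10% slow, 24–60 h) give 0.73–0.94.

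**Step 6: common window.** AUC0-24 on both days returns 1.00 at every half-life tested.

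**The case against.** The best defence is that the SAP names the same interval on both days and schedules matched samples at about 312 h. With those in use, or with extrapolation of a one-compartment curve, the shortfall largely disappears. That is correct, and it makes the problem conditional. It does not remove it. The SAP leaves use of the sparse samples open and does not specify extrapolation for AUC0-tau. At half-lives of 8–12 h the 312 h level is below one ten-millionth of Cmax, so the Day 70 sample could not realistically help, while the 72 h level could well be measurable.

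Three stronger readings are tempting, and the documents do not support them:
- **That the ratio is always biased downward.** Step 4 shows it can be 1.00 or above 1, depending on which late samples are quantifiable and used.
- **That extrapolation never helps.** It largely repairs a one-compartment curve, though it can overshoot. It fails for the biphasic curves.
- **That real accumulation would be masked.** Every scenario above has a true ratio of 1. With linear kinetics, a true ratio of 1.10 needs a half-life near 194 h. The 312 h level would then be about 2^(−312/194) = 0.33 of its initial value, so the Day 70 sample would probably be detectable.

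It is also fair that Rac is not the only evidence on accumulation. The Cmax ratio, the predose levels on Days 29 and 57, and AUC to a fixed time by day are unaffected, and the PK analysis is mainly descriptive. Protocol 9.4.3.3 refers to a PK Analysis Plan that might contain a partial-area rule. That plan is not among the documents, and the SAP's own definition should not depend on it.

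**Conclusion.** The point holds in conditional form. When the Day 1 72 h sample is quantifiable and the Day 70 sample is BLQ or unused, the AUC accumulation ratio understates an unchanged exposure: by 5–6% at a 5 h half-life, 14–17% at 8 h, 26–29% at 12 h and 45–48% at 24 h. These figures assume one-compartment kinetics, an absorption half-life of 1–2 h and error-free data. The size in this trial cannot be determined from the documents. The practical risk is that falling exposure is reported when none occurred. The Cmax ratio is not affected.

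**What to change.** In SAP Table 4-1, define Rac(AUC) as AUC0-24 on Day 57 over AUC0-24 on Day 1, using the shared nominal times (0, 1, 2, 4, 6, 8 and 24 h). Define Day 29 over Day 1 in the same way, and keep Rac(Cmax). Add Rac to Table 3-2, where AUC to 24 h already appears.

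If an AUC0-tau ratio is also wanted, compute it only for participants whose last quantifiable nominal time is the same on both days. Replace the open wording on the Day 14, 42 and 70 samples with a fixed rule. Give the last quantifiable time beside any Day 57 CL/F or Vz/F based on AUC0-tau, and interpret those values with the same caution.

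The cost is one changed definition plus these clarifications, with no new samples or visits. The downside is that the AUC0-24 ratio says nothing about accumulation after 24 h, which the Day 57 schedule cannot reliably measure in any case.

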4.12.3 Statistical Analysis of Pharmacokinetic Parameters

We will use a one-way analysis of variance to compare the PK parameters of ALDH2 mutation. If there are 3 or more subjects with ALDH2 mutation, the PK parameters of these subjects as a group will be compared to those without ALDH2 mutation as another group. Otherwise, the PK parameters will be summarized with and without the individual(s) with ALDH2 mutation.

Sample SAS Code:

```
PROC MIXED DATA = DATA1 NOPRINT;
BY PARAMCD;
CLASS MUTATION;
MODEL LN_PK = MUTATION /DDFM = KR;
RUN;
```

WHERE,

PARAMCD :short name of PK parameter

LN_PK; natural log transformed value of PK parameter
MUTATION: Group for the genetic mutation.

4.12.4 Pharmacodynamic Analysis, Concentration, and Parameter TFLs, and Statistical Analysis of Pharmacodynamic Parameters

Pharmacodynamic parameters will be estimated according to the guidelines presented in Table 4-2.

Table 4-2 Pharmacodynamic Parameter and Estimation

Parameter	Guidelines for Derivation
Cmax, tmax,	Obtained directly from the observed concentration-time data
C_{av}	The average concentration from time 0 to time 4 h: $AUC_{0-4\text{ h}}$
$AUC_{0-4\text{ h}}$ -adjusted	The AUC adjusted from zero time to 4 h for Day X: $AUC_{0-4\text{ h}}(\text{Day X}) - AUC_{0-4\text{ h}}(\text{Day -1})$
C_{av} -adjusted	The C_{av} adjusted for Day X is time averaged concentration from zero time to 4 h: $C_{av}(\text{Day X}) - C_{av}(\text{Day -1})$
Cmax-adjusted	The Cmax adjusted for Day X is: $C_{max}(\text{Day X}) - C_{max}(\text{Day -1})$
$AUC_{0-4\text{ h}}$ percent change	Percent change of $AUC_{0-4\text{ h}}$ on Day X as compared to the basal level (Day -1): $((AUC_{0-4\text{ h}}(\text{Day X}) - AUC_{0-4\text{ h}}(\text{Day -1})/\text{day -1})) \times 100$
C_{av} percent change	Percent change of C_{av} on Day X as compared to the basal level (Day -1): $((C_{av}(\text{Day X}) - C_{av}(\text{Day -1})/\text{day -1})) \times 100$
Cmax percent change	Percent change of Cmax on Day X as compared to the basal level (Day -1): $((C_{max}(\text{Day X}) - C_{max}(\text{Day -1})/\text{day -1})) \times 100$

Individual participant's biomarker (acetaldehyde, acetate, and ethanol) plasma concentration values (baseline unadjusted values only) will be provided by [REDACTED] Laboratories and [REDACTED]. Baseline unadjusted and adjusted acetaldehyde, acetate, and ethanol concentration values will be listed by study day, timepoint, ALDH2 mutation, and participant for the PP by [REDACTED]. Concentration listings will include nominal biomarker sampling time, actual sampling times relative to dose administration, and percentage change from baseline. The corresponding baseline for each timepoint will be taken on Day -1. For the biomarker concentration summary tables, descriptive statistics (N, n, arithmetic

mean, SD, CV%, geometric mean, gCV%, median, IQR (inter quartile range), minimum, and maximum values) will be presented by study day, nominal timepoint, EIA days, and ALDH2 mutation. For time variables only median, T_{min} and T_{max} will be presented. A by participant listing of ALDH2 mutation will be provided.

To visualize the comparison between study days the descriptive biomarker graphs will be generated.

- Figure x.x.x: Individual Participant Profiles for acetaldehyde, acetate, and ethanol, Plasma Concentration Time Data (Unadjusted and Adjusted for Baseline) by study day and EIA day (SP)
- Figure x.x.x: Overlaid Individual Participant Profiles for acetaldehyde, acetate, and ethanol Plasma Concentration Time Data (Unadjusted and Adjusted for Baseline) by study day and EIA day (SP). The profiles for ALDH2 mutation will be plotted with dotted lines.
- Figure x.x.x: Mean (\pm SD) baseline adjusted acetaldehyde, acetate, and ethanol Plasma Concentration Time Data by study day and EIA day (PP)
- Figure x.x.x: Mean (\pm SD) baseline adjusted acetaldehyde, acetate, and ethanol Plasma Concentration without ALDH2 Mutant Time Data by study day and EIA day (PP)
- Figure x.x.x: The Mean (\pm SD) baseline unadjusted acetaldehyde, acetate, and ethanol Plasma Concentration Time profiles by study day and EIA days (PP)
- Figure x.x.x: The Mean (\pm SD) baseline unadjusted acetaldehyde, acetate, and ethanol Plasma Concentration without ALDH2 Mutant Time profiles by study day and EIA days (PP)
- Figure x.x.x: The mean (\pm SD) C_{max} (in the units of μ M and ng/mL) and AUC_{0-4h} (in the unit of ng* h /mL) of acetaldehyde, acetate, and ethanol following 4 Alcohol Drinks in 60 Minutes and Multiple Dose Administration of DCR AUD in Healthy Adults will be plotted with EIA days by study day (PP)
- Figure x.x.x: The mean (\pm SD) C_{max} (in the units of μ M and ng/mL) and AUC_{0-4h} (in the unit of ng* h /mL) without ALDH2 Mutant(s) of acetaldehyde, acetate, and ethanol following 4 Alcohol Drinks in 60 Minutes and Multiple Dose Administration of DCR AUD in Healthy Adults will be plotted with EIA days by study day (PP)

For each figure, participants belonging to each category will be shown on the same plot with separate figures for each treatment arm. Participant level figures will use actual time, while mean plots will use planned time, except for pre-dose time point(s), where time 0 will be used rather than actual time.

